## **12 Data analysis and statistical methods**

Any data analysis carried out independently by the investigator should be submitted to Novartis before publication or presentation.

### **12.1 Analysis sets**

The following analysis sets will be used for the statistical analyses:

- Screened set (SCR): All patients who signed the informed consent for the extension open-label study.
- Safety Set (SAF): All SCR patients who received at least one dose of open-label study treatment during the extension open-label study.

### **12.2 Subject demographics and other baseline characteristics**

In the following, the term "age group" refers to the two age groups. Summary statistics will be provided by age group (6 years and older, 1 year to < 6 years) and for overall for demographics and baseline characteristics, including age, age group (only for overall), sex, race, ethnicity, weight, height and vital signs.

Continuous variables will be summarized using n, mean, standard deviation, median, minimum, and maximum. Categorical variables will be summarized using frequencies and percentages.

Relevant medical histories will be summarized, by system organ class and preferred term, for overall and for each age group.

The SAF will be used for the above analyses.

### **12.3 Treatments**

Duration of exposure to the study treatment will be summarized for each age group and for overall, using mean, standard deviation, median, minimum, and maximum. Additionally, the number and percentage of patients in meaningful duration categories will be summarized for each age group and for overall.

Concomitant medications and significant non-drug therapies prior to and after the start of the study treatment will be summarized by anatomical therapeutic classification (ATC), preferred term, for overall and for each age group.

The SAF will be used for the above analyses.

### **12.4 Analysis of the primary endpoint(s)**

The primary objective is to evaluate safety and tolerability of LCZ696 in eligible heart failure patients from PANORAMA-HF receiving open-label investigational drug.

The primary safety assessment will be based on adverse events, which will be analyzed using frequencies and percentages.

The following adverse events will be summarized by primary system organ class, preferred term, and maximum severity as appropriate, for each age group and for overall, using numbers and percentages of patients with at least one adverse event in the corresponding class.

- Any adverse event (treatment emergent or not)
- Any serious adverse event (treatment emergent or not)
- Treatment emergent adverse event (TEAE)
- Treatment emergent serious adverse event
- Treatment emergent adverse event of special interest, i.e. hyperkalemia, hypotension, angioedema, renal impairment
- TEAE leading to dose adjustment, temporary dose interruption, or permanent discontinuation (including death) of study treatment
- TEAE leading to permanent discontinuation (including death) of study treatment

For overall and for each age group, death during the treatment period and the primary cause of death will be summarized using frequencies and percentages.

For overall and for each age group, the vital signs and the laboratory evaluations will be summarized by visit.

Adverse events (including SAEs), laboratory assessments, vital signs, and duration of drug exposure are considered primary endpoints.

#### **12.4.1 Definition of primary endpoint(s)**

Adverse events, laboratory assessments, vital signs, and duration of drug exposure are considered primary endpoints.

#### **12.5 Analysis of secondary endpoints**

Not applicable. There are no secondary endpoints.

#### **12.6 Analysis of exploratory endpoints**

Not applicable. There are no exploratory endpoints.

#### **12.7 Interim analyses**

No interim analysis is planned. However, the safety will be monitored through regular review of adverse events and related data.

#### **12.8 Sample size calculation**

##### **12.8.1 Primary endpoint(s)**

All patients who have completed the double-blind phase of the study PANORAMA-HF, as defined in the Inclusion Criteria ([Section 5.1](#)), and who meet all other Inclusion and Exclusion criteria ([Section 5.1](#) and [Section 5.2](#)), are eligible for the extension study.

There is no specific sample size required for the study.

##### **12.8.2 Secondary endpoint(s)**

Not applicable.

### **13 Ethical considerations and administrative procedures**

#### **13.1 Regulatory and ethical compliance**

This clinical study was designed and shall be implemented, executed and reported in accordance with the ICH Harmonized Tripartite Guidelines for Good Clinical Practice, with applicable local regulations (including European Directive 2001/20/EC, US CFR 21), and with the ethical principles laid down in the Declaration of Helsinki.

#### **13.2 Responsibilities of the investigator and IRB/IEC**

Before initiating a trial, the investigator/institution must obtain approval/favorable opinion from the Institutional Review Board/Independent Ethics Committee (IRB/IEC) for the trial protocol, written informed consent form, consent form updates, subject recruitment procedures (e.g. advertisements) and any other written information to be provided to subjects. Prior to study start, the investigator is required to sign a protocol signature page confirming his/her agreement to conduct the study in accordance with these documents and all of the instructions and procedures found in this protocol and to give access to all relevant data and records to Novartis/sponsor monitors, auditors, Novartis/sponsor Quality Assurance representatives,

designated agents of Novartis/sponsor, IRBs/IECs, and regulatory authorities as required. If an inspection of the clinical site is requested by a regulatory authority, the investigator must inform Novartis/sponsor immediately that this request has been made.

### **13.3 Publication of study protocol and results**

The protocol will be registered in a publicly accessible database such as clinicaltrials.gov and as required in EudraCT. In addition, after study completion (defined as last patient last visit) and finalization of the study report the results of this trial will be submitted for publication and posted in a publicly accessible database of clinical trial results, such as the Novartis clinical trial results website and all required Health Authority websites (e.g. Clinicaltrials.gov, EudraCT etc.).

For details on the Novartis publication policy including authorship criteria, please refer to the Novartis publication policy training materials that were provided to you at the trial investigator meetings.

### **13.4 Quality Control and Quality Assurance**

Novartis maintains a robust Quality Management System (QMS) that includes all activities involved in quality assurance and quality control, to ensure compliance with written Standard Operating Procedures as well as applicable global/local GCP regulations and ICH Guidelines.

Audits of investigator sites, vendors, and Novartis systems are performed by auditors, independent from those involved in conducting, monitoring or performing quality control of the clinical trial. The clinical audit process uses a knowledge/risk-based approach.

Audits are conducted to assess GCP compliance with global and local regulatory requirements, protocols and internal Standard Operating Procedures (SOPs), and are performed according to written Novartis processes.

## **14 Protocol adherence**

This protocol defines the study objectives, the study procedures and the data to be collected on study participants. Additional assessments required to ensure safety of subjects should be administered as deemed necessary on a case by case basis. Under no circumstances including incidental collection is an investigator allowed to collect additional data or conduct any additional procedures for any purpose involving any investigational drugs under the protocol, other than the purpose of the study. If despite this interdiction prohibition, data, information, observation would be incidentally collected, the investigator shall immediately disclose it to Novartis and not use it for any purpose other than the study, except for the appropriate monitoring on study participants.

Investigators ascertain they will apply due diligence to avoid protocol deviations. If an investigator feels a protocol deviation would improve the conduct of the study this must be considered a protocol amendment, and unless such an amendment is agreed upon by Novartis and approved by the IRB/IEC and health authorities, where required, it cannot be implemented.

## **14.1 Protocol amendments**

Any change or addition to the protocol can only be made in a written protocol amendment that must be approved by Novartis, health authorities where required, and the IRB/IEC prior to implementation.

Only amendments that are required for subject safety may be implemented immediately provided the health authorities are subsequently notified by protocol amendment and the reviewing IRB/IEC is notified.

Notwithstanding the need for approval of formal protocol amendments, the investigator is expected to take any immediate action required for the safety of any subject included in this study, even if this action represents a deviation from the protocol. In such cases, Novartis should be notified of this action and the IRB/IEC at the study site should be informed according to local regulations.

## 16 Appendices

### 16.1 Appendix 1: Clinically notable laboratory values and vital signs

**Table 16-1 Clinically notable laboratory values**

Parameter	Conventional Alert Value	Conventional Units	SI Alert Value	SI Units
Hematology				
Red Blood Cell Count	>50% increase, >30% decrease	$\times 10^6/\mu\text{L}$	>50% increase, >30% decrease	$\times 10^{12}/\text{L}$
Hemoglobin	>50% increase, >30% decrease, or any value <7	g/dL	>50% increase, >30% decrease, or any value <70	g/L
Hematocrit	>50% increase, >30% decrease	%	>50% increase, >30% decrease	L/L
White Blood Cell Count	>50% increase, >50% decrease	$\times 10^3/\mu\text{L}$	>50% increase, >50% decrease	$\times 10^9/\text{L}$
Platelet Count	>75% increase, >50% decrease	$\times 10^3/\mu\text{L}$	>75% increase, >50% decrease	$\times 10^9/\text{L}$
Chemistry				
BUN	>50% increase	mg/dL	>50% increase	mmol/L
Creatinine	>50% increase	mg/dL	>50% increase	umol/L
Albumin	<2	g/dL	<20	g/L
Glucose	>50% increase, >50% decrease, or any value <60	mg/dL	>50% increase, >50% decrease, or any value <3.3	mmol/L
Total Bilirubin	>100% increase	mg/dL	>100% increase	umol/L
AST (SGOT)	>150% increase	U/L	>150% increase	U/L
ALT (SGPT)	>150% increase	U/L	>150% increase	U/L
Sodium	>5% increase, or any value >150	mEq/L	>5% increase, or any value >150	mmol/L
Potassium	>20% increase, >20% decrease, or any value >5.3	mEq/L	>20% increase, >20% decrease, or any value >5.3	mmol/L
Chloride	>10% increase, >10% decrease	mEq/L	>10% increase, >10% decrease	mmol/L
Calcium	>10% increase, >10% decrease	mg/dL	>10% increase, >10% decrease	mmol/L
Uric Acid	>50% increase	mg/dL	>50% increase	mmol/L

**Table 16-2 Criteria for clinically notable vital signs**

Age	HR [min]	SBP [mmHg]	DBP [mmHg]	RR [min]
1-3 years	<60, >120	<76, >115	<45, >75	<14, >35
3-6 years	<55, >120	<82, >120	<50, >80	<12, >30
6-12 years	<50, >105	<90, >130	<50, >80	<10, >27
>12 years	<45, >95	<90, >145	<55, >90	<8, >23

## 16.2 Appendix 2: Liver event and laboratory trigger definitions and follow-up requirements

**Table 16-3 Liver event and laboratory trigger definitions**

	Definition/ threshold
LIVER LABORATORY TRIGGERS	
 
• <math>3 \times \text{ULN} < \text{ALT} / \text{AST} \leq 5 \times \text{ULN}</math>
 
• <math>1.5 \times \text{ULN} < \text{TBL} \leq 2 \times \text{ULN}</math>
 

LIVER EVENTS	
 
• ALT or AST <math>> 5 \times \text{ULN}</math>
 
• ALP <math>> 2 \times \text{ULN}</math> (in the absence of known bone pathology)
 
• TBL <math>> 2 \times \text{ULN}</math> (in the absence of known Gilbert syndrome)
 
• ALT or AST <math>> 3 \times \text{ULN}</math> and INR <math>> 1.5</math>
 
• Potential Hy's Law cases (defined as ALT or AST <math>> 3 \times \text{ULN}</math> and TBL <math>> 2 \times \text{ULN}</math> [mainly conjugated fraction] without notable increase in ALP to <math>> 2 \times \text{ULN}</math>)
 
• Any clinical event of jaundice (or equivalent term)
 
• ALT or AST <math>> 3 \times \text{ULN}</math> accompanied by (general) malaise, fatigue, abdominal pain, nausea, or vomiting, or rash with eosinophilia
 
• Any adverse event potentially indicative of a liver toxicity*
 

\*These events cover the following: hepatic failure, fibrosis and cirrhosis, and other liver damage-related conditions; the non-infectious hepatitis; the benign, malignant and unspecified liver neoplasms

TBL: total bilirubin; ULN: upper limit of normal

**Table 16-4 Follow-up requirements for liver events and laboratory triggers**

Criteria	Actions required	Follow-up monitoring
Potential Hy's Law case a	
 
• Discontinue the study treatment immediately
 
• Hospitalize, if clinically appropriate
 
• Establish causality
 
• Complete liver eCRF
 
	ALT, AST, TBL, Albumin (Alb), PT/INR, ALP and γGT until resolution c (frequency at investigator discretion)
ALT or AST		
$> 8 \times \text{ULN}$	
 
• Discontinue the study treatment immediately
 
• Hospitalize if clinically appropriate
 
• Establish causality
 
• Complete liver eCRF
 
	ALT, AST, TBL, Alb, PT/INR, ALP and γGT until resolution c (frequency at investigator discretion)
$> 3 \times \text{ULN}$ and INR $> 1.5$	
 
• Discontinue the study treatment immediately
 
• Hospitalize, if clinically appropriate
 
• Establish causality
 
• Complete liver eCRF
 
	ALT, AST, TBL, Alb, PT/INR, ALP and γGT until resolution c (frequency at investigator discretion)

Criteria	Actions required	Follow-up monitoring
> 5 to $\leq$ 8 $\times$ ULN	
 
Repeat LFT within 48 hours
 
If elevation persists, continue follow-up monitoring
 
If elevation persists for more than 2 weeks, discontinue the study drug
 
Establish causality
 
Complete liver eCRF
 
	ALT, AST, TBL, Alb, PT/INR, ALP and $\gamma$ GT until resolution c (frequency at investigator discretion)
> 3 $\times$ ULN accompanied by symptoms b	
 
Discontinue the study treatment immediately
 
Hospitalize if clinically appropriate
 
Establish causality
 
Complete liver eCRF
 
	ALT, AST, TBL, Alb, PT/INR, ALP and $\gamma$ GT until resolution c (frequency at investigator discretion)
> 3 to $\leq$ 5 $\times$ ULN (patient is asymptomatic)	
 
Repeat LFT within the next week
 
If elevation is confirmed, initiate close observation of the patient
 
	Investigator discretion Monitor LFT within 1 to 4 weeks
ALP (isolated)		
> 2 $\times$ ULN (in the absence of known bone pathology)	
 
Repeat LFT within 48 hours
 
If elevation persists, establish causality
 
Complete liver eCRF
 
	Investigator discretion Monitor LFT within 1 to 4 weeks or at next visit
TBL (isolated)		
> 2 $\times$ ULN (in the absence of known Gilbert syndrome)	
 
Repeat LFT within 48 hours
 
If elevation persists, discontinue the study drug immediately
 
Hospitalize if clinically appropriate
 
Establish causality
 
Complete liver eCRF
 
	ALT, AST, TBL, Alb, PT/INR, ALP and $\gamma$ GT until resolution c (frequency at investigator discretion) Test for hemolysis (e.g. reticulocytes, haptoglobin, unconjugated [indirect] bilirubin)
> 1.5 to $\leq$ 2 $\times$ ULN (patient is asymptomatic)	
 
Repeat LFT within the next week
 
If elevation is confirmed, initiate close observation of the patient
 
	Investigator discretion Monitor LFT within 1 to 4 weeks or at next visit
Jaundice	
 
Discontinue the study treatment immediately
 
Hospitalize the patient
 
Establish causality
 
Complete liver eCRF
 
	ALT, AST, TBL, Alb, PT/INR, ALP and $\gamma$ GT until resolution c (frequency at investigator discretion)
Any AE potentially indicative of a liver toxicity	
 
Consider study treatment interruption or discontinuation
 
Hospitalization if clinically appropriate
 
Establish causality
 
	Investigator discretion

Criteria	Actions required	Follow-up monitoring
	

• Complete liver eCRF

	

aElevated ALT/AST > 3 × ULN and TBL > 2 × ULN but without notable increase in ALP to > 2 × ULN  
b(General) malaise, fatigue, abdominal pain, nausea, or vomiting, or rash with eosinophilia  
cResolution is defined as an outcome of one of the following: (1) return to baseline values, (2) stable values at three subsequent monitoring visits at least 2 weeks apart, (3) remain at elevated level after a maximum of 6 months, (4) liver transplantation, and (5) death.

## 16.3 Appendix 3: Specific renal alert criteria and actions

**Table 16-5 Specific renal alert criteria and actions**

Serum event	
Estimated GFR* decrease ≥ 25% compared to baseline AND eGFR < 90 mL/min/1.73m 	Confirm ≥ 25% decrease AND eGFR* < 90 mL/min/1.73m  after 24-48 hours (h). If it persists, follow up with repeat, if possible, within 2-5 days. Then do some frequent monitoring (preferably weekly) until event resolves or stabilizes. If event does not resolve or stabilize, consider consulting nephrologist and/or drug interruption. Follow up within 24-48h if possible. If value persists, consider consulting nephrologist and/or drug interruption.
Acute Kidney Injury: Serum estimated GFR* decrease ≥50% compared to baseline in the PANORAMA-HF core study (i.e. Visit 301 for Part 2)	
Urine event	Confirm by urinary protein creatinine ratio. If it persists, consider consulting nephrologist and/or drug interruption.
New dipstick proteinuria ≥ 1+	Confirm value after 24-48 h, if possible. If dipstick value confirmed: a) perform urinary protein/creatinine ratio (PCR) within 2-5 days, if possible. If PCR > 0.2 then: b) perform urine microscopy and evaluate. If PCR > 0.2 and /or urine microscopy has findings (e.g. crystals, casts, dysmorphic RBC, leukocytes), consider consulting nephrologist or drug interruption or discontinuation
New dipstick glucosuria ≥ 1+ not due to diabetes	Confirm value after 24-48 h, if possible. If it persists: a) perform, blood glucose (fasting) b) perform urinary protein/creatinine ratio. If PCR ratio > 0.2 and blood glucose abnormal consider consulting nephrologist and /or drug interruption or discontinuation
New dipstick hematuria ≥ 1+ not due to trauma	Confirm value after 24-48 h, if possible. If it persists: a) perform urinary protein creatinine ratio (PCR) within 2-5 days on a first morning urine collection b) perform urine microscopy and evaluate. If PCR > 0.2 and /or urine microscopy has findings (e.g. crystals, casts , dysmorphic RBC, leukocytes) consider consulting nephrologist or drug interruption or discontinuation

\* eGFR is calculated using a modified Schwartz formula for subjects <18 years:

eGFR (ml/min/1.73m^2) = 0.413 x height (cm) / serum creatinine (mg/dl). The most recently available height should be used for calculation.

Urine samples for testing for renal monitoring, and particularly those for the PCR ratio determination, must be collected at the first morning void.

Document contributing factors in the eCRF: co-medication, other co-morbid conditions, and additional diagnostic procedures performed.

Monitor patient regularly (frequency at investigator's discretion) until either:

Event resolution: estimated GFR within 20% of baseline and  $> 90 \text{ mL/min}/1.73\text{m}^2$  or PCR  $< 0.2$ ;

Event stabilization: estimated GFR within 20% of baseline OR  $> 90 \text{ mL/min}/1.73\text{m}^2$  or PCR  $< 0.3$ .

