If the laboratory abnormality induces clinical signs or symptoms, or requires therapeutic intervention, and satisfies the criteria defined in [Section 10](#) Safety reporting, then the diagnosis or medical condition must be entered on the AEs page of the subject's eCRF and any treatment necessary should be documented. If the laboratory abnormality is the primary reason for an unforeseen hospitalization or otherwise fulfills the seriousness category of an AE, then the procedure for rapid notification of SAEs must be followed.

Likewise, if the laboratory abnormality leads to discontinuation of the study drug, the subject must be followed until the abnormality resolves or until it is judged to be permanent. This investigation may include continued monitoring by repeat laboratory testing or by performing additional laboratory tests as deemed necessary by the investigator or the Sponsor's medical monitor.

For child bearing potential females only, serum pregnancy testing will be performed at screening (visit 500), and End of Study visit (Visit 599). Please see details in [Section 8.4.2](#).

A table, which provides the maximum, allowable blood-draw volumes by weight, can be found in [Appendix 8](#).

There are countries where plasma potassium is used instead of serum potassium for routine clinical care. Plasma potassium can be used instead of serum potassium in this study. Serum potassium thresholds in the study protocol, including those values cited in [Appendix 1](#) and [Appendix 7](#) can be converted to plasma potassium thresholds for the study by subtracting 0.4 mmol/L from the serum potassium threshold.

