6. its outcome

Conditions that were already present at the time of informed consent should be recorded in medical history of the subject.

Adverse events (including lab abnormalities that constitute AEs) should be described using a diagnosis whenever possible, rather than individual underlying signs and symptoms.

Adverse event monitoring should be continued for at least 30 days following the last dose of study treatment.

Once an adverse event is detected, it must be followed until its resolution or until it is judged to be permanent (e.g. continuing at the end of the study), and assessment must be made at each visit (or more frequently, if necessary) of any changes in severity, any potential relationship to the interventions required to treat it, and the outcome.

Information about adverse drug reactions for the investigational drug can be found in the Investigator's Brochure (IB).

Abnormal laboratory values or test results constitute adverse events only if they fulfill at least one of the following criteria:

- they induce clinical signs or symptoms
- they are considered clinically significant
- they require therapy

Clinically significant abnormal laboratory values or test results must be identified through a review of values outside of normal ranges/clinically notable ranges, significant changes from baseline or the previous visit, or values which are considered to be non-typical in subjects with the underlying disease. Alert ranges for laboratory and other test abnormalities are included in [Appendix 1](#).

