#### Action situation

If a patient eGFR\* decreases by  $\geq 50\%$  from baseline of the core study (i.e. Visit 301 for Part 2) (or if serum creatinine concentration rises above 3 mg/dL (265  $\mu$ mol/L), the investigator will check for potentially reversible causes of renal dysfunction (see above). If the investigator judges that study medication has to be stopped, he/she will have to contact the Novartis medical monitor or his/her designee. Thereafter, serum creatinine assessments will have to be repeated at least each week until levels return to acceptable values. If study medication was stopped, every effort will be done to restart it again, according to clinical conditions.

\*eGFR is calculated using a modified Schwartz formula for subjects  $<18$  years.

For subjects  $\geq 18$  years, an adult formula for eGFR will be utilized (Reference: Novartis Nephrology Guidance document)

[figure not shown]

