Renal impairment	
1. Standard analyses;
 
2. For serum creatinine and eGFR, the test values and changes from baseline will be summarized by visit, age group and overall using number of observations, mean, standard deviation, median, minimum, Q1, Q3, and maximum; the summaries will be provided for local and central lab separately;
 
3. Numbers and percentages of patients with the following events will be provided by age group and overall (the summaries will be provided for local and central lab together and if both central lab and local lab data are available, central lab result will take precedence over local lab result):
 
• eGFR decline by >25%, >40%, >50%, and/or >30 mL/min/1.73 m² (postbaseline assessments comparing to baseline) and <LLN;• eGFR < 45 mL/min/1.73 m² and/or eGFR < 30 mL/min/1.73 m²• Serum creatinine increase by >50% (post-baseline assessments comparing to baseline) and >ULN;• Serum creatinine increase by >0.5 mg/dL and >ULN (post-baseline assessments comparing to baseline),• serum creatinine post-baseline >2.0 mg/dL, >2.5 mg/dL, >3.0 mg/dL ;• Standard analyses within the subgroups additionally if possible: patients with baseline eGFR ≤170 mL/min/1.73 m² and >170 mL/min/1.73 m².

For safety topics of special interest defined in the CRS, the standard analyses will be performed.

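### Appendix 3 lets a kidney-injury alert count as stabilized, and regular monitoring end, while eGFR is still at or below half of its Visit 301 value

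*Protocol*

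**What the plan says.** **Opening the event.** The kidney-injury row of Table 16-5 (protocol Appendix 3) is an eGFR fall of at least 50% "compared to baseline in the PANORAMA-HF core study (i.e. Visit 301 for Part 2"). It has no absolute eGFR limit. The other serum row needs a fall of at least 25% and also an eGFR below 90; it says only baseline, without naming a visit.

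**Acting on it.** A follow-up sample is requested within 24 to 48 hours if possible, and then: "If value persists, consider consulting nephrologist and/or drug interruption". The cells of Table 16-5 run together in the text I have read, so assigning this step to the kidney-injury row is an inference from its position and wording.

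**Closing it.** The text below Table 16-5 asks for regular monitoring, at a frequency the investigator sets, until resolution or stabilization. Resolution needs eGFR within 20% of baseline and above 90, or PCR below 0.2. Stabilization is looser: "Event stabilization: estimated GFR within 20% of baseline OR" above 90, or PCR below 0.3. This text covers the table as a whole, and Section 10.2.2 refers every Table 16-5 event to Appendix 3 for follow-up.

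**The concern.** The alert is relative and one of its closing criteria is absolute, so at a high enough baseline both can be true of one eGFR value. The closing rule also asks for a level and not for a repeat, an interval or an unchanged value. The liver appendix (Table 16-4, footnote c) is more demanding where it relies on stability, since one of its routes to resolution is "stable values at three subsequent monitoring visits at least 2 weeks apart".

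The 25% row is protected by its own below-90 condition; the kidney-injury row is not. At an eGFR above 90 the kidney-injury row is also the only serum alert in Table 16-5 that can fire.

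What is at stake is site follow-up in a study where Section 4.5 names renal impairment as one of four possible safety risks. Once extra monitoring stops in the maintenance phase, Section 8.4.1 schedules complete and abbreviated laboratories each every 12 months, offset by 6 months, so the next planned creatinine can be up to about 6 months away.

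**Working it through.** The plan gives no figure to reproduce, so this is a direct check of the rules.

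**Inputs.** B is Visit 301 eGFR and S is the current sample, both in mL/min/1.73 m². From Appendix 3:
- Kidney-injury alert: S ≤ 0.5B.
- 25% alert, taken on the same baseline: S ≤ 0.75B and S < 90.
- Stabilization, eGFR criteria: 0.8B ≤ S ≤ 1.2B, or S > 90.
- Resolution, eGFR criteria: 0.8B ≤ S ≤ 1.2B and S > 90.

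**Step 1: kidney-injury alert against stabilization.** The within-20% criterion needs S ≥ 0.8B and cannot hold with S ≤ 0.5B. The above-90 criterion can: 90 < S ≤ 0.5B has solutions only if 0.5B > 90, that is B > 180. The width of the overlap is B/2 − 90.

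| Visit 301 eGFR | Samples meeting both rules | Width |
|---|---|---|
| 180 or lower | none | 0 |
| 190 | above 90, up to 95 | 5 |
| 200 | above 90, up to 100 | 10 |
| 220 | above 90, up to 110 | 20 |
| 240 | above 90, up to 120 | 30 |

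At B = 240 the fall can approach 1 − 90/240 = 62.5%. A fall to 90 or lower is not stabilized on this criterion.

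**Step 2: the other pairings.** The 25% alert never overlaps: S < 90 rules out S > 90, and S ≤ 0.75B rules out S ≥ 0.8B. The kidney-injury alert never overlaps the eGFR criteria for resolution.

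**Step 3: the PCR alternative.** Taken literally, PCR below 0.3 is sufficient by itself. A fall from 120 to 55 is (120 − 55)/120 = 54.2%; with a PCR of 0.1 it would be stabilized, and even resolved, since 0.1 is below 0.2. The limit of 180 therefore assumes that PCR is meant for urine events only.

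**Step 4: plausibility of B > 180.** The protocol formula is eGFR = 0.413 × height/creatinine. At 100 cm, an eGFR of 180 is a creatinine of 0.413 × 100/180 = 0.229 mg/dL, and any lower creatinine gives a higher eGFR. SAP Table 2-3 plans "Standard analyses within the subgroups additionally if possible: patients with baseline eGFR" at or below 170 and above 170. The sponsor therefore allows for high values, though on the SAP baseline and not on Visit 301.

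**Step 5: a different baseline at closure.** The closing rule does not name its baseline. Visit 301, which opened the alert, is the more natural choice. If a site used the extension baseline O instead, S ≤ 0.5B and S ≥ 0.8O could both hold when O ≤ (0.5/0.8)B = 0.625B. As an assumed example, with B = 120, O = 70 and S = 60, the falls are 60/120 = 50.0% and 10/70 = 14.3%. Such a child would already be 50/120 = 41.7% down at entry.

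**The case against.** **Other rules still protect the child.** This is the strongest reply, and most of it stands.
- The 24-to-48-hour follow-up and the persistence step apply, though the first is qualified by feasibility and the second asks only for consideration.
- Appendix 4 requires a search for reversible causes at the same 50% fall from Visit 301. It adds that "serum creatinine assessments will have to be repeated at least each week until levels return to acceptable values". That sentence directly follows the one on stopping study medication, so it may or may not cover children who stay on drug.
- Under Section 10.1.1, once an adverse event is detected "it must be followed until its resolution or until it is judged to be permanent". This applies only if the laboratory change is symptomatic, clinically significant or treated.
- Under Section 8.4.1, if the abnormality leads to discontinuation, "the subject must be followed until the abnormality resolves or until it is judged to be permanent".
- At unchanged height a halved eGFR is a doubled creatinine (at 100 cm, 0.217 to 0.435 mg/dL for 190 to 95). Against the same baseline this exceeds the 50% rise in Table 16-1 and must be commented on.

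None of these clearly prevents a site from ending regular monitoring under Appendix 3 while the alert criterion is still met.

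**Monitoring until an end state looks forward.** A reader might infer that the sample which opens the event is meant to close it. The documents do not go that far: the row's own follow-up step points to a second sample. But that second sample may also be above 90 and at or below half of baseline, and it would then close the event.

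**An eGFR above 90 is a defensible level for calling a child stable.** It matches the limit in the 25% row. That is reasonable as a clinical choice, but it does not fit an alert that has no such limit.

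**The liver comparison proves little.** Footnote c defines resolution, and three-visit stability is only one of its routes. It shows that a repeat requirement is familiar in this protocol, not that the renal rule must copy it.

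**Conclusion.** The point holds as a minor inconsistency in a safety-monitoring rule. On the eGFR criteria with Visit 301 as the common baseline, the alert and stabilization coincide only when Visit 301 eGFR exceeds 180 and the sample is above 90 and at or below half of baseline. The limit of 180 is exact, but it rests on reading PCR as a urine-event criterion.

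Stronger conclusions a reader might draw are not supported:
- That children will be left unmonitored. The documents give no Visit 301 values and no count of children above 180, and the safeguards listed above remain.
- That the problem reaches ordinary eGFR values. This needs either the literal PCR reading or the less natural choice of the extension baseline at closure. In the second case, inclusion criterion 2 and exclusion criterion 9 may keep out a child already 41.7% down.
- That reported results are affected. SAP Section 2.8.3 counts falls of 50% or more and does not analyse stabilization.

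**What to change.** Change Appendix 3 only, by adding three statements to the closing rule:
- (a) A kidney-injury event may be called stabilized or resolved only on a repeat sample taken after the alert, with eGFR less than 50% below Visit 301, unless it is judged permanent (an exit Section 10.1.1 already allows).
- (b) The PCR criteria apply to urine events only.
- (c) Closure uses the same baseline as the alert: Visit 301 for the kidney-injury row and Visit 500 for the 25% row. Visit 500 is the visit Table 3-1 uses for eGFR reduction.

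Statement (a) moves the above-90 closing line to above 95, 100 and 110 for Visit 301 values of 190, 200 and 220. At 180 or lower, on the eGFR criteria and a common baseline, it changes nothing: a sample above 90 is already above half of baseline, and the alert sample could not close the event anyway.

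This does not impose a plateau. From 190, a repeat of 96 (94/190 = 49.5% down) would still close the event. It ensures only that closure rests on a later sample that no longer meets the alert. A rule of several stable visits would go further, at the price of more blood draws.

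The cost is a few extra creatinine repeats in affected children, at the frequency the investigator already sets. Appendix 4 and the SAP stay as they are.
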